| Study Description: | We will determine whether N-of-1 trials, as a pragmatic, patient-centered approach to medication optimization that can overcome key barriers of deprescribing, can lead to increased subject confidence regarding the decision to continue or discontinue beta-blockers in older adults with Heart Failure with Preserved Ejection Fraction (HFpEF). |
| Sample Size: | N=16 |
| Enrollment: | This study will enroll 16 subjects. |
| Study Population: | Subjects will be recruited from the HFpEF Program, as well as from the Cardiology, Heart Failure, Geriatrics and/or Internal Medicine clinics at Weill Cornell Medicine. |
| Enrollment Period: | 30 Months |
| Study Design: | This is an unblinded NIH Stage 1 of Behavioral Intervention Development trial, using a Crossover intervention model. We will enroll 16 subjects and we will conduct four rounds of N-of-1 trials with four subjects each. We will use a two-arm crossover titration/reversal design (On [A] vs. Off [B]) with up to 4 periods. Subjects will be randomized to either ABAB or BABA (see Figure 1 below). Each period will last up to 6 weeks, allowing for sufficient time for up-titration and onset of drug action, and down-titration and washout. Each subject will have the option to participate in less (2-3) or more periods (5-6) depending on whether they need additional information to make an informed decision about continuing or discontinuing their beta-blocker at the end of this trial. The intervention drug will be beta-blockers, previously prescribed to the subjects by their physician. We have developed a titration algorithm, where we will reduce the dose of each beta-blocker by 50% every week. |
| Description of Sites/ Facilities Enrolling | |
| Subjects: | Enrollment will only be at Weill Cornell Medicine. |
| Study Duration: | Estimated Primary Completion Date of December 2022 |
| Subject Duration: | 1 Year |
| Study Agent/Device Name | Not applicable |

Intervention Description:

The intervention is a two-arm crossover withdrawal/reversal design (On [A] vs. Off [B]) with up to 4 periods, each period lasting up to 6 weeks. During the On period (A), subjects will be on their beta-blocker. During the Off period (B), their beta-blockers will be down-titrated and subsequently discontinued; we will decrease the dose of beta-blocker by 50% every week regardless of which beta-blocker they are on, similar to an algorithm used in a prior deprescribing trial. Subjects will be randomized to either ABAB or BABA (see Figure 1 below).

Subjects may be on any of the following beta-blockers:

- Atenolol
- Betaxolol
- Bisoprolol
- Metoprolol
- Metoprolol Succinate
- Metoprolol Tartrate
- Penbutolol
- Nebivolol
- Propranolol
- Acebutolol
- Pindolol
- Carvedilol
- Labetalol
- Nadolol
- Sotalol
- Nadolol

Co-Primary Objectives:

To determine the features of a feasible and pragmatic protocol for deprescribing N-of-1 trials in patients with Heart Failure with Preserved Ejection Fraction.

Funded by National Institute on Aging

To compare physical activity between the On and Off phase via:

- Step Count collected via Garmin wearable device

Funded by the New York Community Trust

To compare exercise capacity between the On and Off phase via:

- Peak oxygen consumption (VO₂) Cardiopulmonary Exercise Test

Funded by the New York Community Trust

To compare lower extremity function between the On and Off phase via:

- Short physical performance battery (lower extremity function)

Funded by the New York Community Trust

Secondary Objective:

To compare Patient Reported Outcomes between the On and Off phase via:

- Kansas City Cardiomyopathy Questionnaire
- PRO Measurement Information System including PROMIS-29, PROMIS-Sexual Function, PROMIS-SF 6a and EQ5D Visual Analogue Scale (VAS)

Funded by the New York Community Trust

Exploratory Objectives:

We will explore whether N-of-1 trials can improve decision-making parameters, including decision conflict (measured by the Decision Conflict Scale), patient activation (measured by the Patient Activation Measure), Shared Decision Making (measured by the 9-item Shared Decision-Making Questionnaire), and attitudes toward deprescribing (measured by the revised patient attitudes toward deprescribing questionnaire).

Funded by National Institute on Aging

Primary Endpoints:

The features of a feasible and pragmatic protocol for deprescribing N-of-1 trials as measured by qualitative interviews.

Funded by the National Institute on Aging

All of the below endpoints are being funded by the New York Community Trust.

The change in physical activity when on beta-blocker versus when off beta-blocker, as measured by step count on a wearable activity monitoring device.

The change in lower extremity function when on beta-blocker versus when off beta-blocker, as measured by Short Physical Performance Battery

The change in exercise capacity when on beta-blocker versus when off beta-blocker, as measured by peak oxygen consumption (VO₂) during cardiopulmonary exercise test (CPET)

Secondary Endpoints:

All of the below endpoints are being funded by the New York Community Trust.

The change in patient-reported quality of life when on beta-blocker versus when off beta-blocker, as measured by Patient Reported Outcome Measurement System-29 (PROMIS-29)

The change in patient-reported sexual function when on beta-blocker versus when off beta-blocker, as measured by Patient-Reported Outcome Measurement Information System-Sexual Function (PROMIS-Sexual Function)

The change in patient-reported cognitive function when on beta-blocker versus when off beta-blocker, as measured by Patient-Reported Outcome Measurement Information System-Short Form 6a (PROMIS SF-6a)

The change in patient-reported health status when on beta-blocker versus when off beta-blocker, as measured by Kansas City Cardiomyopathy Questionnaire (KCCQ-12)

The change in patient-reported health when on beta-blocker versus when off beta-blocker, as measured by the EuroQol-5d Visual Analogue Scale (EQ-5D VAS)

Exploratory Endpoints:

The impact of N-of-1 trials on decision conflict as measured by the Decision Conflict Scale.

[figure not shown]
The impact of N-of-1 trials on patient activation as measured by the Patient Activation Measure.

The impact of N-of-1 trials on Shared Decision Making as measured by the 9-Item Shared Decision-Making Questionnaire.

The impact of N-of-1 trials on attitudes toward deprescribing as measured by the Revised Patient Attitudes toward Deprescribing Questionnaire.

1.1 Schema

Figure 1. Study Design of a subject with 4 six-week periods

1.2 Study Objectives

1.2.1 Co-Primary Objectives

- To determine the features of a feasible and pragmatic protocol for deprescribing N-of-1 trials in patients with Heart Failure with Preserved Ejection Fraction. (Funded by the National Institute on Aging)
- The change in physical activity when on beta-blocker versus when off beta-blocker, as measured by step count on a wearable activity monitoring device. (Funded by the New York Community Trust)
- The change in lower extremity function when on beta-blocker versus when off beta-blocker, as measured by Short Physical Performance Battery. (Funded by the New York Community Trust)
- The change in exercise capacity when on beta-blocker versus when off beta-blocker, as measured by peak oxygen consumption (VO₂) during cardiopulmonary exercise test (CPET). (Funded by the New York Community Trust)

1.2.2 Secondary Objectives

- The change in patient-reported quality of life when on beta-blocker versus when off beta-blocker, as measured by Patient Reported Outcome Measurement System-29 (PROMIS-29) (Funded by the New York Community Trust)
- The change in patient-reported sexual function when on beta-blocker versus when off beta-blocker, as measured by Patient-Reported Outcome Measurement Information System-Sexual Function (PROMIS-Sexual Function) (Funded by the New York Community Trust)
- The change in patient-reported cognitive function when on beta-blocker versus when off beta-blocker, as measured by Patient-Reported Outcome Measurement Information System-Short Form 6a (PROMIS SF-6a) (Funded by the New York Community Trust)
- The change in patient-reported health status when on beta-blocker versus when off beta-blocker, as measured by Kansas City Cardiomyopathy Questionnaire (KCCQ-12) (Funded by the New York Community Trust)
- The change in patient-reported health when on beta-blocker versus when off beta-blocker, as measured by the EuroQol-5d Visual Analogue Scale (EQ-5D VAS) (Funded by the New York Community Trust)

| Table 1: PRO Administration Details (50 items in total) | | |
|---|------------|-----------------------------|
| Instrument | # of Items | Domain |
| KCCQ-12 | 12 | HF-specific health status |
| PROMIS-29 | 4 | Fatigue |
| | 4 | Depression |
| | 4 | Anxiety |
| | 4 | Sleep |
| | 4 | Physical function |
| | 4 | Social Role |
| | 5 | Pain interference/intensity |
| PROMIS (SF-6a) | 6 | Cognitive function |
| PROMIS-Sexual Function | 2 | Sexual Function |
| EQ-5D Visual Analogue Scale | 1 | Quality of Life |

1.2.3 Exploratory Objectives

- To examine whether N-of-1 trials can improve decision parameters, patient activation, and attitudes toward deprescribing.
 - Decision Conflict Scale (DCS)
 - Patient Activation Measure (PAM)
 - 9-Item Shared Decision-Making Questionnaire
 - revised Patient Attitudes Toward Deprescribing (rPATD)

2. Background

2.1 Disease

Heart Failure with Preserved Ejection Fraction (HFpEF) affects >3 million people across the US and is a prototypical geriatric syndrome—it disproportionately affects older adults (mean age ~76 years); age-related changes to the cardiovascular system and common age-related comorbid conditions are implicated in its pathogenesis; and multiple comorbid conditions and polypharmacy are nearly universal. While beta-blockers are the most commonly used medication for HFpEF (~80% in a recent Randomized Controlled Trial), there is substantial uncertainty regarding their benefits in HFpEF. Although the benefits of beta-blockers in Heart Failure with reduced ejection fraction are well-documented, Randomized Clinical Trials (RCTs) of beta-blockers in HFpEF have been neutral to date, failing to consistently improve or worsen long-term outcomes including mortality and hospitalization rates; and short-term effects on patient-reported outcomes like function and quality of life are not well-described, with a signal of harm in some.

2.2 Rationale

High medication burden among older adults with multiple chronic conditions including those with heart failure is a growing problem in the United States that can negatively impact the health and wellbeing of older adults. Deprescribing (or medication discontinuation) has emerged as a strategy to improve outcomes in older adults with multiple chronic conditions and high medication burden but is underutilized. With this project, we will refine an innovative pragmatic subject-centered approach (N-of-1 trials) to medication optimization in older adults, thereby improving the health and wellbeing of older adults with multiple chronic conditions.

In [name] clinical experience as Director of the HFpEF Program for the Aging, he has found that some patients feel better with beta-blockers while others feel worse. This idea is supported by opposing pathophysiologic mechanisms highlighted in the literature—on the one hand, beta-blockers can slow down heart rate, improve left ventricular filling, and thus improve cardiac output and overall functioning. On the other hand, beta-blockers can exacerbate chronotropic incompetence, worsen cardiac output, and reduce exercise tolerance. Beta-blockers are also a common cause of adverse drug reactions and can worsen function in some older adults. There is no readily discernable way to determine which patients will feel better and which will feel worse. Although the benefits of beta-blockers in HF with reduced ejection fraction are well documented, RCTs of beta-blockers in HFpEF have been neutral to date, failing to consistently improve or worsen long-term outcomes including mortality and hospitalization rate. Thus, beta-blocker use in HFpEF is a well-suited and clinically relevant model for developing a subject-centered approach to medication optimization.

N-of-1 trials offer a potentially transformative approach to deprescribing. Unlike traditional population-based clinical trials, N-of-1 trials are conducted within a single subject, using multiple crossover design experiments to compare different treatments.

2.3 Risk/Benefit Assessment

The risks and benefits of N-of-1 trials relate directly to the risks of initiation and discontinuation of beta-blockers.

2.3.1 Known Potential Risks

All subjects:

- i) Risks associated with down-titration/discontinuation of beta-blocker: Adverse drug withdrawal events including tachycardia, worsened hypertension, palpitations, diaphoresis, shortness of breath, heart failure exacerbation, angina, myocardial infarction, cerebrovascular accident, arrhythmia, hospitalization, and death (shown to occur with abrupt cessation of beta-blocker)
- ii) Risks associated with beta-blocker use (and re-initiation/up-titration): Adverse drug events or adverse drug reactions including bradycardia, heart block, hypotension, dizziness, fatigue, depression, confusion, heart failure exacerbation, cerebrovascular accident, hospitalization, and death
- iii) Risks associated with wearing the Garmin wearable device: Local skin irritation, wrist pain
- iv) Risks associated with subject interviews: Emotional distress related to answering interview questions, and breach of confidentiality
- v) Risks associated with Cardiopulmonary Exercise Test and Short Physical Performance Battery: musculoskeletal injury, arrhythmias, acute coronary syndrome, hemodynamic instability, cardiovascular collapse, death.
- vi) Risks associated with Short physical performance battery: falling, musculoskeletal injury.
- vii) Risks associated with the 6-minute walk test: fatigue, dizziness.
- viii) Risks associated with blood draws: pain or bruising, dizziness, infection at the site of the blood draw

2.3.2 Known Potential Benefits

For some, continuing beta-blockers may be beneficial: Beta-blockers slow down heart rate, improve left ventricular filling and thus improve cardiac output and overall functioning. They can function as anti-hypertensive and may suppress arrhythmias.

For others, stopping beta-blockers may be beneficial: Beta-blockers can exacerbate chronotropic incompetence, worsen cardiac output, and reduce exercise tolerance. Beta-blockers are also a common cause of adverse drug reactions and can worsen function in some older adults. Beta-blockers can also contribute to undesirable symptoms like fatigue and sexual dysfunction.

Subjects may specifically benefit from this study by gaining insight on the individual-level short-term effects of beta-blockers. This information could then help subjects determine whether they wish to continue or discontinue beta blockers, potentially contributing to increased decision confidence and subject activation, and possibly improving quality of life.

2.3.3 Assessment of Potential Risks and Benefits

Rationale to exposing subjects to risk

- 1.) Exposure to beta-blocker: Subjects are already on beta-blocker at the time of recruitment; thus, being on beta-blocker does not explicitly add additional risk beyond usual clinical care
- 2.) Down-titration/discontinuation: Subjects will have their beta-blocker dose decreased and/or discontinued. There is limited data to support the benefits of beta-blocker in HFP EF, despite its frequent use. Moreover, beta-blocker use poses several harms in older adults including bradycardia, heart block, hypotension, dizziness, fatigue, depression, confusion, heart failure exacerbation, cerebrovascular accident, hospitalization and death. Accordingly, down-titration/discontinuation of beta-blocker may actually be safer than continuing beta-blocker, at least in some.

To mitigate the risks of down-titration/discontinuation, we will incorporate the following:

- 1.) remote monitoring protocol that includes assessments of resting heart rate and blood pressure
- 2.) telephone calls made by the research team to the subject on the day before a dose modification is planned, to instruct about the next day's dose change; the day a dose modification is planned, to confirm the dose change was made and the assess health status; and the day following dose modification, to reassess health status, where we will ascertain whether the subject is experiencing any withdrawal effects such as chest pain, tachycardia, palpitations, diaphoresis, and shortness of breath, as well as any adverse events, such as hospitalizations and/or adverse cardiovascular events, including HF exacerbation, myocardial infarction, arrhythmia, cerebrovascular accident and death; based off of subject feedback, telephone calls may be eliminated during the last 2 weeks of each period
- 3.) We will also provide a 24 hour/7 day per week hotline for subjects to call if they develop any concerning symptoms. Importantly, we will exclude subjects with other indications for beta-blocker use to maximize safety. For example, individuals with hypertrophic cardiomyopathy will be excluded, since beta-blockers have a clear benefit in this condition (and are a Class I indication).

We hypothesize that there will be benefits to dose reduction (down-titration/discontinuation). Beta-blockers can exacerbate chronotropic incompetence, worsen cardiac output, and reduce exercise tolerance, as well as possibly worsen physical function, and be a major cause of adverse drug reactions. [name] (as a board-certified heart failure physician and HFP EF specialist) has already observed this in his clinical practice—among nine subjects in whom he has discontinued beta-blockers, 8 of the 9 felt better.

The justification of risk is that this study has the potential to lead to a paradigm shift in the way beta-blockers are used in HFP EF. We believe beta-blockers are overused in this subtype of heart failure and may be causing more harm than good in the many HFP EF subjects.

In addition, all inclusion and exclusion criteria were selected to ensure we exclude subjects with other evidence-based indications for beta-blockers. In other words, we excluded subjects who may be harmed if we stop beta-blockers.

3. Study Design

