|  | In-Office visit |
|  | Conducted Remotely |
|  | Conducted via Telephone |
|  | Collected via Garmin wearable device |

⁵ Decision Making Parameters Questionnaire to consist of Decision Conflict Scale, Decision Conflict Subscales, Patient Activation Measures Survey, Shared Decision-Making Questionnaire (SDM-1-9) and Revised Patient Attitudes Towards Deprescribing (rPATD)

⁶ Telephone contact to occur the day prior to, the day of, and the day following a dose modification. Telephone calls may be eliminated per subject feedback during the last two weeks of each period.

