6.1.2 Treatment Phase

6.1.2a Daily

- Remote Monitoring
 - Remote monitoring will collect vital sign data, including blood pressure and heart rate via a free of charge remote monitoring platform already in use in the HFpEF Program. Data will be reviewed weekly. If we encounter “Red Flags”, we will call the subject to assess symptoms, and determine the need for medical attention and/or study withdrawal in consultation with the subject’s other physicians and the DSMB.
 - Red Flags are as follows:
 - Blood pressure >160/90 mmHg or <100/60 mmHg
 - Heart Rate >100 bpm or <50 bpm
- Step Count
 - Daily step count will be collected via Garmin wearable devices that will be provided to subjects during the duration of the treatment phase of the trial.

6.1.2b Weekly

- Dose modification (as described in section 3.1)
- Telephone Contact on the day prior to the dose modification, the day of the dose modification and on the day following dose modification. Telephone calls may be eliminated during the last 2 weeks of each period per subject feedback.
- Patient Reported Outcomes (PROMIS-29, PROMIS-SF 6A) via web-based surveys taken at home on tablet computers provided to each subject, over the phone, or via email – frequency/length of surveys may be decreased per subject feedback
- Interim Events History (Adverse Events/SAE) will be asked during each phone call

6.1.2.c Biweekly

- Kansas City Cardiomyopathy Questionnaire (KCCQ-12)

6.1.2d End of Periods

- Medication Inventory
- Dose Modification
- Physical Exam, including vital signs
- Central blood pressure assessment via the UScom BP+ device, when possible
- Electrocardiogram
- Six Minute Walk Test
- Cardiopulmonary Exercise Test (at the end of Period 1 and Period 2)
 - We may draw additional blood for Troponin & NT-proBNP directly after the CPET. On visits which include a CPET, the subject may have Troponin and NT-proBNP drawn twice.
- Blood Draw for Troponin & NT-proBNP
- Blood draw for future research (at end of period 1 & end of period 2 only)
- Short Physical Performance Battery
- Qualitative interview on understandability and usability of study materials
- EQ-5D VAS
- PROMIS-29
- PROMIS-SF 6A
- PROMIS-Sexual Function

- Kansas City Cardiomyopathy Questionnaire (KCCQ-12)
- Interim Events History

6.1.2e End of Intervention Visit Period

- Medication Inventory
- Dose Modification
- Physical Exam
- Central blood pressure assessment via the UScom BP+ device
- Electrocardiogram
- Six Minute Walk Test

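### The calls around dose changes name 11 of 12 listed withdrawal risks but only 4 of 11 listed re-initiation risks, so the two kinds of symptom may be elicited unevenly

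*Combined protocol and SAP*

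**What the plan says.** Section 2.3.1 keeps two separate risk lists. For stopping, item (i) gives "Adverse drug withdrawal events including tachycardia, worsened hypertension, palpitations, diaphoresis, shortness of breath, heart failure exacerbation, angina, myocardial infarction, cerebrovascular accident, arrhythmia, hospitalization, and death". For use and restarting, item (ii) gives "bradycardia, heart block, hypotension, dizziness, fatigue, depression, confusion, heart failure exacerbation, cerebrovascular accident, hospitalization, and death".

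The calls are introduced in section 2.3.3 under the words "To mitigate the risks of down-titration/discontinuation, we will incorporate the following". Three calls surround each planned change: one the day before to give instructions, one on the day to confirm the change and assess health, and one the day after to reassess health. On the last of these, "we will ascertain whether the subject is experiencing any withdrawal effects such as chest pain, tachycardia, palpitations, diaphoresis, and shortness of breath". The same sentence continues: "as well as any adverse events, such as hospitalizations and/or adverse cardiovascular events, including HF exacerbation, myocardial infarction, arrhythmia, cerebrovascular accident and death".

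The calls are not confined to tapering. Footnote 6 of the schedule in section 6.1 reads "Telephone contact to occur the day prior to, the day of, and the day following a dose modification", with no direction specified. Section 6.1.2b adds that "Interim Events History (Adverse Events/SAE) will be asked during each phone call". No section gives separate content for calls during up-titration.

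**The concern.** In this crossover, subjects are taken off a drug and put back on it, and both moves have their own listed harms. The call content was written for the first move and is applied to both. A symptom asked about by name tends to be reported more readily than one the subject must volunteer. The study is also unblinded (section 7.8), so subjects know which way their dose is going.

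Two things are at stake. Dizziness or confusion after an up-titration step may go unrecorded because nobody asks about it. In addition, the DSMB, which reviews data unmasked after each cohort of four (sections 12.5 and 15), may see a balance of On and Off events that partly reflects how the questions were put.

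Section 2.3.3 justifies drug exposure on the ground that subjects are already taking it at recruitment. That does not describe a subject restarting after an Off period.

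**Working it through.** The plan states no figure on this point, so there is none to reproduce. The check is a count.

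**Risks named on the calls.** The inputs are the two lists in 2.3.1 and the full call sentence in 2.3.3, with chest pain counted as angina. The sentence names five symptoms, all described as withdrawal effects, and six events (hospitalization, HF exacerbation, myocardial infarction, arrhythmia, cerebrovascular accident, death): 5 + 6 = 11 items.

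| List | Items | Named | Not named |
|---|---|---|---|
| 2.3.1(i), withdrawal | 12 | 11 | worsened hypertension |
| 2.3.1(ii), use and re-initiation | 11 | 4 | dizziness, confusion, fatigue, depression, hypotension, bradycardia, heart block |

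The four named from (ii) are HF exacerbation, cerebrovascular accident, hospitalization and death. All four are also on list (i), so nothing specific to being on the drug is named. If arrhythmia is read to include bradycardia and heart block, the count is 4 + 2 = 6 of 11, and five remain unnamed.

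**Share of switches that are re-initiations.** The inputs are section 3.1 (everyone enters on the home dose; Arm 1 stays on it in Period 1; Arm 2 tapers in Period 1; 2 to 6 periods) and 1:1 allocation (section 6.1.1). With k periods in both arms, Arm 1 has k − 1 titrated switches and Arm 2 has k, giving 2k − 1 in total. Of these, k − 1 are re-initiations, so the share is (k − 1)/(2k − 1).

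| Periods | Arm 1 tapers / re-initiations | Arm 2 tapers / re-initiations | Pooled share |
|---|---|---|---|
| 2 | 1 / 0 | 1 / 1 | 1/3 = 33% |
| 3 | 1 / 1 | 2 / 1 | 2/5 = 40% |
| 4 | 2 / 1 | 2 / 2 | 3/7 = 43% |
| 5 | 2 / 2 | 3 / 2 | 4/9 = 44% |
| 6 | 3 / 2 | 3 / 3 | 5/11 = 45% |

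With 16 subjects split 8/8 and all completing four periods, that is 24 re-initiations among 56 switches. The minimum is two periods, so every Arm 2 subject who completes it is re-initiated once. So is any Arm 1 subject who completes Period 3.

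**Calls affected.** Section 7.4 says up-titration reverses the taper. Reversing the Table 4 examples gives 3 dose steps (bisoprolol, pindolol), 5 (metoprolol, carvedilol) or 4 (the other eight rows). Two of the three calls per step assess health, so one re-initiation involves 3 × 2 = 6 to 5 × 2 = 10 calls. A four-period Arm 1 subject has one re-initiation (6 to 10 calls) and an Arm 2 subject has two (12 to 20). A fifth up-step would fall in week 5, when calls may be dropped.

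**The case against.** The strongest reply is that this treats prose from a risk section as a call script. The sentence sits under a heading about mitigating taper risk, so withdrawal examples belong there, and they are offered only as examples. The same sentence asks about any adverse events, and section 6.1.2b requires an adverse-event history at every call. A reader might infer that the calls ask about withdrawal effects and nothing else. The documents do not support that.

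Other channels also cover much of list (ii):
- Low pulse and low blood pressure are red flags that trigger a symptom call (sections 3.1 and 6.1.2a).
- PROMIS-29 and PROMIS-SF 6A cover fatigue, depression and cognition weekly.
- An ECG is listed at period-end visits.
- Adverse events are asked about at every visit (section 13.4).
- A hotline is open around the clock.

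All of this stands and narrows the point, but it does not close the gap:
- The adverse-event question is open, while the other state's symptoms are named.
- Vitals are reviewed weekly, and the lower heart-rate flag is below 60 bpm in Table 3 but below 50 bpm in section 6.1.2a. Those two passages must be reconciled.
- Survey frequency may be cut on subject feedback, and no section routes PROMIS scores to the adverse-event log.
- The ECG is omitted at remote visits.
- Dizziness is neither a domain in Table 1 nor a named prompt.

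On the narrowest reading, the withdrawal list belongs to the day-after call alone. The calls that now carry it would then number 3 to 5 per re-initiation.

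**Conclusion.** The imbalance in what the calls name is real: 11 of 12 against 4 of 11, or 6 of 11 on the generous reading. Under-reporting of re-initiation symptoms is a risk that follows from it. A reader might go further and infer that re-initiation harms are in fact being missed, or that the DSMB's data are tilted towards the Off state. The documents do not show this. They give no event rates and no call script, and section 12.4 specifies no On-versus-Off comparison of adverse events.

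A reader might also suppose that half of all titrated switches are re-initiations. That holds for some individual sequences, such as Arm 2 over four periods. Pooled over both arms it is 3 of 7, because Arm 2's opening taper is itself a titrated switch.

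The pooled shares assume equal arms with the same number of periods in each. The call counts assume the home doses in Table 4, and they fall if late-period calls are dropped. The point is a cheap improvement to data collection. It does not show a fault in the results.

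**What to change.** In sections 2.3.3 and 6.1.2b, replace the list of withdrawal symptoms with one fixed checklist covering the effects in both 2.3.1(i) and 2.3.1(ii). Ask it in the same words at every call that assesses health status (the day of and the day after each dose change), whichever way the dose is moving. Keep the open adverse-event question after it. Log each positive answer as an adverse event with the period and dose step, so that On and Off counts rest on the same questions. Items that a subject cannot report directly, such as heart block, need lay wording.

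The cost is about seven more yes/no items per call (eight if worsened hypertension, the one gap in list (i), is included), one REDCap form and a change of protocol wording. The calls themselves are already planned. The downside is slightly longer calls, in a study that is trying to limit contact burden, and more mild events recorded.
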